### **Assessment of Causality**

All solicited administration site and systemic events will be considered causally related to administration of the study intervention. The complete list of these events is provided in [Table 13](#).

Alternative possible causes, such as the natural history of underlying disease, concomitant therapy, other risk factors, and the temporal relationship of the event to the study intervention will be considered and investigated. The investigator will also consult the IB and/or the Summary of Product Characteristics and/or Prescribing Information for marketed products to assist in making his/her assessment. Causality should be assessed by the investigator using the following question:

*Is there a reasonable possibility that the unsolicited AE may have been caused by the study intervention?*

- YES : There is a reasonable possibility that the study intervention contributed to the AE.
- NO : There is no reasonable possibility that the AE is causally related to the administration of the study intervention. There are other, more likely causes and administration of the study intervention is not suspected to have contributed to the AE.

If an event meets the criteria to be determined as “serious”, additional examinations/tests will be performed by the investigator to determine ALL possible contributing factors for each SAE.

Possible contributing factors include:

- Medical history.
- Other medication.
- Protocol required procedure.
- Other procedure not required by the protocol.
- Lack of efficacy of the study intervention, if applicable.
- An error in study intervention administration.

Other cause (specify). There may be situations when an SAE has occurred, and the investigator has minimal information to include in the initial report to IQVIA. However, it is very important to record an assessment of causality for every event before submitting the Expedited AE Report to IQVIA.

The causality assessment is one of the criteria used when determining regulatory reporting requirements. The investigator may change his/her opinion of causality after receiving additional information and update the SAE information accordingly.

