### 3.0 OBJECTIVES AND ENDPOINTS

**Table 5** Study Objectives and Endpoints

Objectives	Endpoints
Primary	

 
To evaluate the immune response of VNS vaccine (formulated with different potencies) and VV vaccine in terms of geometric mean concentration at Day 43
 
	
 
Anti-gE antibody concentration at Day 43
 

Secondary	

 
To evaluate the immune response of VNS vaccine (formulated with different potencies) and VV vaccine in terms of seroresponse rate* at Day 43
 
To evaluate safety and reactogenicity following administration of VNS and VV vaccines
 
	
 
Seroresponse to gE at Day 43
 
 
Solicited events
 
 
Percentage of participants reporting each solicited administration site event in terms of injection site redness, pain and swelling within 4 days (Day 1 to Day 4) post-dose of VNS vaccine or VV vaccine
 
Percentage of participants reporting each solicited systemic event in terms of fever, varicella-like rash†, and general rash (not varicella-like) within 43 days (Day 1 to Day 43) post-dose of study interventions**
 
Percentage of participants reporting each solicited systemic event in terms of drowsiness, loss of appetite, and irritability within 15 days (Day 1 to Day 15) post-dose of study interventions**
 
 
Unsolicited adverse events (AEs)***
 
 
Percentage of participants reporting unsolicited AEs within 43 days (Day 1 to Day 43) post-dose of study interventions**
 
 
Serious adverse events (SAEs)
 
 
Percentage of participants reporting SAEs post-dose of study interventions** up to the end of study
 

AE = adverse event; gE = glycoprotein E; SAE = serious adverse event; VNS vaccine = investigational vaccine, VV vaccine = comparator vaccine (*Varivax*).

\*Seroresponse rate is defined as the percentage of participants for whom post-dose of the study interventions (Day 43), the anti-gE antibody concentration is  $\geq 300$  mIU/mL.

\*\*Study interventions = VNS vaccine (investigational vaccine); VV vaccine (*Varivax*, comparator vaccine); MMR (*M-M-R II* or *M-M-RVaxPro*), *Havrix* and *Prevnar 13* (if applicable) vaccines (co-administered vaccines).

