14. PRIOR, CONCOMITANT AND CO-ADMINISTERED VACCINATIONS

Prior, concomitant and co-administered vaccination will be coded with the current version of the GSK drug dictionary.

- Prior vaccinations are vaccinations per protocol given to participants prior to the dosing of study intervention at Day 1 and are recorded on the eCRF.
- MMR, *Havrix*, and *Prevnar 13* are co-administered with both VNS and VV in this study as

Document: \\quintiles.net\enterprise\Apps\sasdata\SASb\SAS\GlaxoSmithKline\VNS\217212(VNS 20-006)\Biostatistics\Documentation\SAP\ GSK_217212(VNS 20-006)_ZZA47662_SAP_Final_v7_24Jun2024.docx

Author: PPD Version Number: 7.0
Version Date: 24Jun2024

Template No.: CS_TP_BS016 Revision 6

Reference: CS_WI_BS005

Effective Date: 02Dec2019

study interventions.

- Concomitant vaccinations are defined as any vaccine that the participant is receiving as of the time of enrolment or receives during the study (other than study interventions) as recorded on the “Concomitant Vaccination” page of the eCRF.

In addition, if a concomitant vaccination may help explain an AE/SAE, the cause of the AE/SAE or the treatment of an AE/SAE, this information will be recorded under the “Concomitant Medications/Vaccinations Entry” section of the “Expedited Adverse Events (Serious adverse event)” page of the eCRF.

Data will be presented in table summaries for co-administered MMR, *Havrix*, and *Prevnar 13* vaccines, for the ES and in listings for all prior/concomitant and co-administered vaccines.

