18.1.2. UNSOLICITED AEs, INCLUDING SAEs

For each study group, the incidence rates (frequencies and percentages) of participants/events with unsolicited AEs (any, related, grade 3, leading to medical advice and related grade 3 respectively), including serious AE, occurring within 43-days (Days 1-43) post-dose of study interventions at Day 1 will be presented by SOC and PT. The incidence rates of participants/events with any unsolicited AEs will be summarized by country.

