18.1.2.1. Relationship to Study Vaccination

Causality, as indicated by the Investigator is classed as “related” and “not related” to VNS/VV or MMR or *Havrix* or *Prevnar 13*. A “related” AE is defined as an AE with a relationship to study intervention as “related”. If a participant reports the same AE more than once within that SOC/PT, the AE with the worst-case relationship to study intervention will be used in the corresponding relationship summaries for each vaccination group.

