18.1.4. SERIOUS AEs

For each study group, the incidence rates (frequencies and percentages) of participants with SAE occurring post-dose of study interventions at Day 1 will be presented by SOC and PT. Similar tabulation will be done for SAE with causal relationship to vaccination as assessed by the investigator; for fatal SAE and for causally related fatal SAE. Serious AEs will be recorded on the "Expedited Adverse Events" page of the eCRF. The incidence rates of participants with serious AEs will be summarized by country.

Listings of AEs and SAEs leading to discontinuation of study will be provided.

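### The related-AE and related-SAE tables, as specified, mix events attributed to VNS or Varivax with events attributed only to a co-administered vaccine

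*Protocol*

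**What the plan says.** **The question.** Protocol Appendix 4, Assessment of Causality, gives one yes/no question for unsolicited AEs: "Is there a reasonable possibility that the unsolicited AE may have been caused by the study intervention". The YES category reads "There is a reasonable possibility that the study intervention contributed to the AE". Neither answer names a product.

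**What the term covers.** The footnote to Protocol Table 5 begins "Study interventions = VNS vaccine (investigational vaccine" and goes on to list Varivax, MMR, Havrix and, if applicable, Prevnar 13. SAP section 14 agrees: MMR, Havrix and Prevnar 13 "are co-administered with both VNS and VV in this study as" study interventions. Each child therefore receives three or four vaccines under this term.

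**The SAP definition.** SAP 18.1.2.1 says the investigator's causality is classed as related or not related, and lists the varicella vaccine, MMR, Havrix and Prevnar 13 joined by *or*. It then states that a related "AE is defined as an AE with a relationship to study intervention as" related.

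**The tables.** SAP 18.1.2 plans unsolicited AE tables by group, SOC and PT for these categories: "any, related, grade 3, leading to medical advice and related grade 3 respectively". For SAEs, SAP 18.1.4 says "Similar tabulation will be done for SAE with causal relationship to vaccination as assessed by the" investigator, and adds fatal SAEs and causally related fatal SAEs. Neither section specifies a split by causal vaccine.

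**The objective.** The secondary safety objective in Protocol Table 5 is "To evaluate safety and reactogenicity following administration of VNS and VV vaccines".

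**The concern.** Protocol section 2.2 says VNS has not been given to humans before, and section 2.3.1 recognizes that the co-administered vaccines may carry risks of their own. A reader of the related-event tables will want to know what blinded investigators attributed to the new vaccine. The tables as specified answer a wider question: what they attributed to any of the three or four vaccines given that day.

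Attribution after same-day vaccination is not always guesswork. Protocol Table 7 assigns separate sites: varicella vaccine in the left arm, MMR in the right arm, Havrix in the right thigh and Prevnar 13 in the left thigh. The Schedule of Activities solicits administration-site events only for the VNS or VV dose. A local reaction at any other site therefore enters as an unsolicited AE. Its source is plain, yet it would be tabulated as related in the child's VNS potency column. The same holds for a related SAE that the investigator ascribes to a licensed co-administered vaccine.

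**Working it through.** The documents state no figure on this point, so the main check is textual. An illustration then sizes the effect.

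**Step 1. Follow one event through the plan.** Take a Grade 3 local reaction at the MMR site on Day 2.
- It is not solicited, because only VNS/VV site events are (Protocol Schedule of Activities).
- The investigator answers Appendix 4's question YES, because MMR is a study intervention (Table 5 footnote).
- SAP 18.1.2.1 makes it a related AE, because the relationship is to the study intervention.
- SAP 18.1.2 counts it under related and under related grade 3, in the column of the varicella vaccine received.

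An SAE attributed only to a co-administered vaccine takes the same route into the related-SAE table of 18.1.4.

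**Step 2. Size, under assumed rates.** The group size is 200, with VV lots pooled (Protocol 9.2). The event rates are assumptions, since the documents give none. Let p be the proportion of children with an AE related to the varicella vaccine, and c the proportion with an AE related to a co-administered vaccine, the same in every group and independent of p.

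- Composite rate = 1 − (1 − p)(1 − c)
- Risk difference = (1 − c) × (p_VNS − p_VV)
- Wald 95% half-width = 1.96 × √[(r₁(1 − r₁) + r₂(1 − r₂)) / 200], with r₁ and r₂ the two tabulated rates

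With p = 3% (VV) and 6% (VNS), and c = 10%:
- VV: 1 − 0.97 × 0.90 = 12.7%
- VNS: 1 − 0.94 × 0.90 = 15.4%
- Difference: 0.90 × 3.0 = 2.7 points
- Half-width: 1.96 × √[(0.1109 + 0.1303) / 200] = 6.8 points

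| c | VV | VNS | Difference (points) | Ratio | Half-width (points) |
|---|---|---|---|---|---|
| 0 (varicella-specific) | 3.0% | 6.0% | 3.0 | 2.0 | 4.1 |
| 5% | 7.85% | 10.7% | 2.85 | 1.36 | 5.7 |
| 10% | 12.7% | 15.4% | 2.7 | 1.21 | 6.8 |
| 20% | 22.4% | 24.8% | 2.4 | 1.11 | 8.3 |

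**Step 3. Share of related participants with no varicella-attributed event.** This is 1 − p/(composite rate). For the VNS group at c = 10% it is 1 − 6.0/15.4 = 61%. At c = 5% it is 1 − 6.0/10.7 = 44%, and at c = 20% it is 1 − 6.0/24.8 = 76%.

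**Step 4. Sensitivity to p.** With p = 5% (VV) and 10% (VNS) and c = 10%, the composite rates are 14.5% and 19.0%. The difference is 4.5 instead of 5.0 points, and the share is 1 − 10.0/19.0 = 47%. The pattern is the same: the difference hardly moves, while much of the related column need not concern the varicella vaccine.

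**The case against.** The other side has a good deal to say.

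**The data may exist.** SAP section 9 leaves the content of tables and listings to templates, and section 5.4 refers to mock shells. Neither these nor the eCRF are among the documents. The vaccine list in SAP 18.1.2.1 can be read as recording causality per vaccine, and SAP section 7 lists all collected data unless otherwise specified. A reader might infer that product attribution will be unobtainable. The documents do not support that; they show only that the text specifies no such table.

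**No contradiction is proved.** If the SAP's *or* is composite, it agrees with Appendix 4. If it is per vaccine, the data exist and only a table row is missing. A reader might call this a protocol–SAP conflict, but the wording is ambiguous, not contradictory. On either reading, the definition of related that follows is composite.

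**The endpoints are composite too.** Table 5 counts unsolicited AEs and SAEs after the study interventions, and no endpoint is defined by relatedness. This stands: the any-AE and any-SAE tables are untouched.

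**Randomization protects the comparison.** Within a country all groups receive the same co-administered vaccines, and country and center are minimization factors (Protocol 6.3.2). A reader might infer bias for or against VNS. There is none from this source: the same background is added to every group.

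**No contrast is planned.** SAP section 18 excludes statistical comparisons of safety between groups. The fall in the ratio and the wider half-width therefore describe a contrast that a reader might form, not one the plan computes.

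**SAEs are examined case by case.** Appendix 4 requires all possible contributing factors to be sought for each SAE. That helps with individual cases but does not change the tables.

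What remains is that the specified tables are composite, and that a varicella-specific row would add information which investigators can often give, most clearly for local reactions at the other injection sites.

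**Conclusion.** The point holds as a limit on what the planned tables show. As specified, the related unsolicited AE, related Grade 3, related SAE and related fatal SAE tables combine events attributed to VNS/VV with events attributed only to a co-administered vaccine. The cost is product-level attribution for the investigational vaccine and some precision.

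The size depends on assumed rates and on independent attributions. With a co-administered rate of 5% to 20%, the difference of 3.0 points becomes 2.85 to 2.4 points, which is a small change. Over the same range, 44% to 76% of the VNS group's related participants would have no varicella-attributed event. The absolute related rate in a VNS column is thus the figure most open to misreading. How much new work is needed depends on whether the eCRF already records causality per vaccine, which the documents do not settle.

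**What to change.** 1. **Protocol Appendix 4 and SAP 18.1.2.1.** Align the two so that causality is recorded for VNS/VV and for each co-administered vaccine, if the eCRF does not already do so.
2. **SAP 18.1.2 and 18.1.4.** Tabulate *related to VNS/VV* next to *related to any study intervention* for unsolicited AEs, Grade 3 AEs, SAEs and fatal SAEs.
3. **If per-vaccine causality was not collected.** State in the SAP and the report that *related* means related to any study vaccine. SAP version 7.0 is dated 24 June 2024, so new data capture may come too late.

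The cost is a few table rows and possibly one eCRF field per vaccine. Attribution of systemic events among same-day vaccines will be imprecise. Because assessors are blinded, that error should be similar across groups. It is the reason to keep the pooled row beside the specific one.

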### **Medically Attended Visits**

For each solicited and unsolicited AE the participant experiences, the participant’s parent(s)/LAR(s) will be asked if the participant received medical attention (defined as hospitalization, or an otherwise unscheduled visit to or from medical personnel for any reason, including emergency room visits). This information will be recorded in the CRF/paper Expedited Adverse Events Report as applicable/in the eCRF.

### **Assessment of Outcomes**

The investigator will assess the outcome of all unsolicited AEs (including SAEs) recorded during the study as:

- Recovered/resolved.
- Recovering/resolving.
- Not recovered/not resolved.
- Recovered with sequelae/resolved with sequelae.

## Reporting, Follow-up, and Assessment of AEs

Recording AEs and SAEs
All AEs and SAEs should be recorded into the appropriate section of the eCRF, irrespective of intensity or whether or not they are considered intervention-related.
AE and SAE Recording

The participants' parent(s)/LAR(s) will be instructed to contact the investigator immediately should the participants manifest any signs or symptoms they perceive as serious.

When an AE/SAE occurs, it is the responsibility of the investigator to review all documentation (e.g., hospital progress notes, laboratory and diagnostics reports) relative to the event. The investigator will then record all relevant information regarding an AE/SAE in the eCRF. The investigator is not allowed to send photocopies of the participant's medical records to either the sponsor or IQVIA instead of appropriately completing the eCRF. However, there may be instances when copies of medical records for certain cases are requested by the sponsor or IQVIA. In this instance, all participant identifiers will be blinded on the copies of the medical records prior to submission to the sponsor or IQVIA.

The investigator will attempt to establish a diagnosis pertaining to the event based on signs, symptoms, and/or other clinical information. In such cases, the diagnosis should be documented as the AE/SAE and not the individual signs/symptoms.

The Use of eDiary/personal electronic device app
An eDiary will be used in this study to capture solicited administration site or systemic events. The participants' parent(s)/LAR(s) should be trained on how and when to complete the eDiary/enter information into the app. Anyone who measures administration site or systemic events and who will record the event in the eDiary/app should be trained on using the eDiary/app. This training must be documented in the participant's source documents. If any individual other than the participant's parent(s)/LAR(s) is making entries in the eDiary/app, their identity must be documented in the eDiary/app/participant's source documents.

Time Period for Collecting and Recording of AEs and SAEs
All solicited administration site events that occur during 4 days (Day 1 to Day 4), and solicited systemic events that occur during 15 days (Day 1 to Day 15) or 43 days (Day 1 to Day 43), following administration of the study intervention, must be recorded into the eDiary/personal electronic device app, irrespective of intensity. Unsolicited events occurring from Day 1 to Day 43 and SAEs occurring up the end of the study should be recorded into the appropriate section of the eCRF, irrespective of intensity or whether or not they are considered vaccination-related.

Follow-up of AEs and SAEs
After the initial AE/SAE or any other event of interest for the study, the investigator is required to proactively follow each participant at subsequent visits/contacts. All SAEs will be followed until the event is resolved, stabilized, or otherwise explained or the participant is lost to follow-up.
Other non-serious AEs must be followed until the last contact or until the participant is lost to follow-up.
Follow-up During the Study
AEs documented at a previous visit/contact and defined as not recovered/not resolved or recovering/resolving will be reviewed at subsequent visits/contacts until the last visit/contact of the participant.
If the participant dies during participation in the study or during a recognized follow-up period, IQVIA will be provided with any available post-mortem findings, including histopathology.
Follow-up After the Participant is Discharged from the Study
The investigator will provide any new or updated relevant information on previously reported SAE to IQVIA using electronic Expedited AE Report as applicable. The investigator is obliged to perform or arrange for the conduct of supplemental clinical examinations/tests and/or evaluations to elucidate the nature and/or causality of the AE or SAE as fully as possible.
Updating of SAE Information After Removal of Write Access to the Participant's eCRF
When additional SAE information is received after removal of write access to the participant's eCRF, new or updated information should be recorded on the appropriate paper report, with all changes signed and dated by the investigator. The updated report should be faxed to IQVIA as described within the timeframes specified in Section 8.3.1 .

Events Requiring Expedited Reporting to IQVIA:
SAE(s) throughout the study

 
Once the investigator or designee become aware that study participant(s) have experienced an SAE, the investigator or designated study staff must complete information in the electronic Expedited AE Report in the eCRF WITHIN 24 HOURS. The report will always be completed as thoroughly as possible with all available details of the event.
 
Even if the investigator does not have all information regarding an SAE, the report should still be completed within 24 hours. Once additional relevant information is received, the report should be updated WITHIN 24 HOURS. The investigator will always provide an assessment of causality at the time of the initial report.
 
Refer to Section 8.3.1 for the details on timeframes for reporting of SAEs.
 

Grade 3 unsolicited AE(s) at least possibly related to vaccination for the first 200 study participants through their Day 43 follow-up:

 
Once the investigator or designee become aware that study participant(s) have experienced a Grade 3 unsolicited AE considered to be at least possibly related to vaccination, the investigator or designated study staff must complete information in the AE form in the eCRF WITHIN 24 HOURS. The AE form will always be completed as thoroughly as possible with all available details of the event.
 
Even if the investigator does not have all information regarding a Grade 3 unsolicited AE considered to be at least possibly related to vaccination, the AE form should still be completed within 24 hours. Once additional relevant information is received, the AE form should be updated WITHIN 24 HOURS. The investigator will always provide an assessment of causality at the time of the initial completion of the AE form.
 
Refer to Section 8.3.1 for the details on timeframes for reporting of AE(s).
 

SAE Reporting to IQVIA via an Electronic Data Capture Tool

 
The primary mechanism for reporting an SAE to IQVIA will be the electronic Data Capture (EDC) Tool.
 

- If the EDC is unavailable for more than 24 hours, then the study center will use the paper Expedited AE Report.
- The study center staff will enter the SAE data into the EDC as soon as it become available.
- After the study is completed at a given site, the EDC will be taken offline to prevent the entry of new data or changes to existing data.
- If a study center receives a report of a new SAE from a participant or receives updated data on a previously reported SAE after the EDC has been taken offline, then the study center can report this information on a paper Expedited AE Report (see the next section) or to the Medical Monitor by phone.
- Contacts of the Medical Monitor for SAE reporting can be found in the SRM.

